3.5 Dose Escalation and Stopping Rules

The decision to proceed to the next dose level will be made after the first three patients in a cohort have completed 56 days (2 cycles) of dosing (from Cycle 1 Day 1). Prior to advancing/changing dose levels, a cohort summary will be completed and submitted to the IND Medical Monitor for review and approval.

Dose de-escalation decisions will be made in accordance with a standard “3+3” study design using the rules below:

Table 7.

Number of Patients with DLT* at a Given Dose Level (assessed independent for each of arm)	De-Escalation Decision Rule
0 out of 3	Enter 3 more patients at this dose level
≥ 2	Dose de-escalation will occur. This dose level will be declared the maximally administered dose (highest dose administered). Three additional patients will be entered at the next lowest dose level.
1 out of 3	Enter at least 3 more patients at this dose level. If 0 of these 3 patients experience DLT, then this is the maximum tolerated dose (MTD). If 1 or more of this group suffer DLT, then dose de-escalation will occur. Three additional patients will be entered at the next lowest dose level.
MTD: The highest dose at which no more than 1 of 6 evaluable patients has had a DLT. Six patients should be treated before the dose is declared the MTD.	

Dose de-escalation will occur at the planned dose levels until the MTD is determined. The MTD is defined as the highest dose level with less than 2 patients with DLT out of at least six patients in the cohort. The recommended Phase 2 dose (RP2D) will be based on safety and preliminary efficacy data from the dose escalation and dose expansion cohorts.

All patients will be treated at the highest current dose level. All enrolled participants will be considered in the DLT analysis. If a DLT occurs in a cohort with 3 patients within first 56 days (from Cycle 1 Day 1), 3 additional patients will be enrolled in that cohort. If at any time more than or equal to one third (33%) of the participants at a dose level experience DLT, the MTD will be reassessed and the next lowest dose level for the combination therapy will be considered the MTD.

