3.2.4 Arm D: Avelumab + Utomilumab (4-1BB) + Radiation

In the dose escalation phase, the dose of radiation will be de-escalated in combination with fixed doses of utomilumab (4-1BB) and avelumab to evaluate the safety, tolerability, and MTD in patients with advanced solid tumors.

Once the MTD or RP2D is determined, the Arm D MTD expansion will enroll up to 14 patients at the previously established safe dose for additional safety and correlative studies to establish the RP2D for this combination.

Radiation will be administered to 1-3 metastatic sites. This will be de-escalated from a total of 24 Gy to 21 Gy. The technique will be stereotactic radiation via intensity-modulated radiation therapy (IMRT) or Volumetric modulated arc therapy (VMAT). The radiation lead-in will occur within Days -5 to -1 with a +/- 3 day window. There will be 3 fractions or days of radiation. In all cases, the radiation must initiate and end within the radiation lead-time. Cycle 1 Day 1 study drug treatment should begin within 3 days of last dose of radiation.

Utomilumab (4-1BB) will be administered at the fixed flat dose of 100 mg IV on Day 1 of each 28-day cycle or every 4 weeks. Avelumab will be administered at the fixed dose of 10 mg/kg IV on Day 15 of Cycle 1 and Days 1 and 15 of each subsequent 28-day cycle or every 2 weeks. Premedications will be administered per institutional standard.

On days when both avelumab and utomilumab are administered, avelumab will be administered first.

Patients will be restaged at the end of every two cycles and tumor response evaluation will be based on RECIST 1.1 and irRECIST. Patients may be allowed to continue treatment after two cycles of avelumab combinations if there is continued clinical response or disease stabilization and patients do not have significant toxicities. Following radiation, a patient may continue treatment on this combination therapy until the patient experiences confirmed disease progression, unacceptable adverse event(s), intercurrent illness that prevents further administration of treatment, and/or treatment is discontinued following investigator's decision to withdraw the patient, pregnancy, patient withdraws consent, noncompliance with trial treatment or procedure requirements, or administrative reasons.

Table 6: Dosing for Arm D: Avelumab + Utomilumab (4-1BB) + Radiation

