Dose Level	Radiation Days -5 to -1	Utomilumab (4-1BB) IV Every 4 Weeks Starting Cycle 1 Day 1	Avelumab IV Every 2 Weeks Starting Cycle 1 Day 15
1 (Start)	24 Gy in 8 Gy / fraction for 3 fractions	100 mg	10 mg/kg
-1	21 Gy in 7 Gy/ fraction for 3 fractions	100 mg	10 mg/kg

As of Amendment Version 09, the avelumab and radiation dosing for Arm D was revised; therefore, the dose de-escalation was re-started.

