9.2 Statistical Methods and Properties

As of Amendment Version 09, this study will be conducted in 4 arms. Arms A, B, and C will each enroll an MTD expansion cohort. Arm D will have a dose de-escalation and MTD.

In Arm D, standard 3 +3 dose de-escalation and MTD will be applied for dose level 1 and -1 with standard MTD and DLTs rule. We will use CTCAE criteria to capture adverse events related to the study drugs. If cohort 1 is not tolerable, there will be de-escalation to cohort -1.

Each study treatment arm will have an MTD expansion cohort of up to 14 patients each. The expansion cohort for each arm will be stopped early if the aggregate DLT rate $> 33\%$ for that particular arm. The aggregate DLT rate for each arm will include patients that were treated at the same dose level in the dose escalation or de-escalation phase. If the trial does not stop early, we will estimate the disease control rate and the response rate separately for each cohort with appropriate 95% confidence intervals. We will also estimate the progression free survival (PFS) and overall survival (OS) distributions using the Kaplan-Meier product limit method and report summary measures such as the median value and probabilities at selected times (again with appropriate 95% confidence intervals).

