9.3 Sample Size Determination

During the course of the study, two to three dose levels were to be examined in each combination arm during the dose escalation/de-escalation with a standard “3+3” design, and a total of 3-6 patients will be enrolled per dose level. After each escalation or MTD determination by Pfizer, there will be an MTD expansion cohort of up to 14 patients each.

Prior to Amendment Version 05, Arm C was designed to have an escalation and 4 patients were enrolled; however, Pfizer provided recommendations for the MTD and requested that the MTD expansion commence. As of Amendment Version 06, the avelumab dosing for Arms A-C was revised; therefore, a new cohort of 14 patients each are expected to be enrolled for the MTD expansions of Arms A-C. As of Amendment Version 07, the original Arm G escalation and expansion (N= 32 total patients) cohorts have been removed from the study due to inability to accrue patients. Prior to Amendment Version 06, there was a total of 31 patients treated in the MTD expansions on the previous avelumab dosing schedule (Arm A: 8; Arm B: 12; Arm C: 11).

As of Amendment Version 08, the dosing schedules for Arms D-F were revised; therefore, Arms D, E, and F were re-initiated with the new schedule. Prior to Amendment Version 08, there were 11 patients enrolled on Arms D-F (Arm D: 4; Arm E: 3; Arm D: 4).

As of Amendment Version 09, the dosing schedule for Arm D was revised; therefore, Arm D dose de-escalation was to be re-initiated with the new schedule (2 dose levels of up to 6 patients each, or up to 12 patients total). Arms E and F were discontinued. Prior to Amendment Version 09, there were 20 patients enrolled on Arms D-F (Arm D prior to Amendment Version 08: 4 and Arm D on Version 08: 3; Arm E prior to Amendment Version 08: 3 and Arm E on Version 08: 3; and Arm F prior to Amendment Version 08: 4 and Arm F on Version 08: 3).

Thus, the planned maximum number of patients for the dose escalation/ de-escalation phase is 36 patients as indicated in Table 12. The planned maximum number of patients for the MTD expansion phase is 92 as indicated in Table 12. Therefore, the planned total maximum accrual in this study will be 128 patients (Escalation 36 + MTD

Expansions 92). Due to screen failures and replacement of inevaluable patients, up to 250 patients may be consented to this trial.

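### Section 3.5 sets the Arm D MTD by two incompatible rules; its closing one-third rule can name as MTD a level with no patients on the current schedule, or a level that does not exist

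*Combined protocol and SAP*

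**What the plan says.** **Levels.** Section 3.2.4 says of the Arm D radiation dose: "This will be de-escalated from a total of 24 Gy to 21 Gy". Table 6 in that section has two rows, level 1 (the start) and level -1 ("21 Gy in 7 Gy/ fraction for 3 fractions"). Section 9.2 describes one step: "If cohort 1 is not tolerable, there will be de-escalation to cohort -1". Section 9.3 budgets the restarted de-escalation as "2 dose levels of up to 6 patients each, or up to 12 patients total".

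**Table 7 (Section 3.5).** After two or more DLTs, or after one DLT in three followed by any DLT in the next group, the action is to de-escalate: "Three additional patients will be entered at the next lowest dose level". No row treats the lowest level differently. The bottom row defines the MTD as the highest dose with at most 1 DLT in 6 evaluable patients and adds: "Six patients should be treated before the dose is declared the MTD". Sections 3.1.1 and 3.4 give the same definition, fewer than two patients with a DLT out of at least six.

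**Closing sentence of Section 3.5.** "If at any time more than or equal to one third (33%) of the participants at a dose level experience DLT", then "the MTD will be reassessed and the next lowest dose level for the combination therapy will be considered the MTD". It sets no condition on data at that lower level.

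**Expansion.** Sections 3.3 and 9.2 stop an arm's expansion cohort when its aggregate DLT rate exceeds 33%, counting patients treated at the same dose during escalation or de-escalation.

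**The concern.** Estimating the MTD in Arm D is a primary objective (Section 2.1.1), and Section 3.5 is where it is decided. One rule there makes the MTD depend on six patients observed at the level named. The other hands the title to the level below because the level above did badly, whatever has or has not been seen below. With two levels, the second rule has only two possible results, and neither satisfies the first rule unless level -1 happens to have been studied already.

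Table 7 adds a smaller gap. Its step down has no destination from level -1, and the section continues de-escalation until an MTD is determined, as if one must be found. The outcome in which neither level qualifies is not described.

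At stake is what the trial reports as the Arm D MTD, and whether two people applying Section 3.5 to the same counts would report the same answer.

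**Working it through.** **1. Number of levels.** Table 6 and Section 9.2 give two. Section 9.3's budget reproduces: 2 levels × 6 patients = 12. It leaves no patients for a third level.

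**2. The two MTD rules side by side.**

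| Where the one-third trigger is met | Level named by the closing sentence | Patients there on the current schedule | Meets Table 7's six-patient requirement? |
|---|---|---|---|
| Level 1, in de-escalation or expansion, before -1 is opened | -1 | 0 (Section 3.2.4 says de-escalation was restarted at Amendment 09) | No |
| Level -1 | none defined | none possible | No |

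**3. Chance that a level fails under Table 7.** Reading the two-or-more row as cumulative at a level, and since 0 of 3 also leads to three more patients, a level passes only with at most 1 DLT in 6. For a true DLT probability p:

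P(fail) = 1 − (1 − p)^6 − 6p(1 − p)^5.

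Worked at p = 0.25: 1 − 0.1780 − 0.3560 = 0.466. Enumerating the three-then-three sequence gives the same values. The protocol states no p, so a range is shown.

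| p, same at both levels | P(one level fails) | P(both fail) = P(fail)² |
|---|---|---|
| 0.10 | 0.114 | 0.013 |
| 0.15 | 0.224 | 0.050 |
| 0.20 | 0.345 | 0.119 |
| 0.25 | 0.466 | 0.217 |
| 0.30 | 0.580 | 0.336 |
| 0.33 | 0.642 | 0.412 |
| 0.40 | 0.767 | 0.588 |
| 0.50 | 0.891 | 0.793 |

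If the rate is lower at -1: 0.30 then 0.20 gives 0.580 × 0.345 = 0.20; 0.40 then 0.30 gives 0.767 × 0.580 = 0.44. The middle column is also the chance, once -1 is opened, that Table 7 orders a step that cannot be taken.

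**4. Chance that the closing sentence is triggered in an expansion.** Start from 0 or 1 DLT in the first six and add 14 patients one at a time (patients 7 to 20). One third is reached at 3 DLTs for n = 7–9, 4 for 10–12, 5 for 13–15, 6 for 16–18 and 7 for 19–20. With 33% read as 0.33, the expansion stop needs the same counts at every n. The probability of reaching them at some point is 1.7%, 12.9%, 36.7% and 64.8% at p = 0.10, 0.20, 0.30 and 0.40. When this happens in an expansion at level 1, Section 3.3 stops the cohort and the closing sentence of Section 3.5 names -1 as MTD.

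**The case against.** The strongest reply is that the protocol as a whole already prevents the bad outcome. De-escalation is confined to planned levels, and only two are planned. The 12-patient budget has no room for a third. The IND Medical Monitor must approve a cohort summary before any change of level, and Section 9.3 has the IND Office review every three evaluable patients in Arm D. A failed level -1 cannot meet the MTD definition, and the expansion opens only once an MTD is determined (Section 3.1.2). Section 13.0 allows termination for drug safety problems. It can be added that the closing sentence begins by saying the MTD will be reassessed, which suggests judgement.

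Much of this stands. Table 7's silence at -1, taken alone, would be little more than missing detail. It does not answer the closing sentence, which goes on from reassessment to state the result, and that result conflicts with the six-patient requirement in the same section.

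Three stronger readings are tempting and are not supported:

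- *Arm D has no workable stop at level -1.* The gap is in the de-escalation phase only. An expansion at -1 is stopped above 33% (Sections 3.3 and 9.2).
- *Table 7's step-down sentence itself moves the MTD.* It moves patients. Only the closing sentence of Section 3.5 moves the MTD.
- *The closing sentence opens a 14-patient expansion at an unobserved level.* Arm D has one expansion of up to 14. Table 12's Arm D total of 33, less 4, 3 and 12, leaves 14, and slots used at level 1 are not restored. The six-patient requirement also stands against it.

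Nor does a hidden third level rescue the rule. Section 9.3 mentions two to three levels per arm, and Table 1's Arm D maximum of 32 equals 3 × 6 + 14, whereas two levels give 12 + 14 = 26. No third Arm D level is defined anywhere.

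**Conclusion.** The concern holds as an internal contradiction on a primary objective. Followed literally, the closing sentence of Section 3.5 can declare as MTD a level with no patients on the current schedule, or an undefined level, while Table 7 in the same section requires six treated patients with at most one DLT. Separately, and less seriously, Table 7's step down cannot be carried out at level -1 during de-escalation, and the outcome of a failure there is not stated.

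With equal true DLT rates, both levels fail with probability about 1% at 10%, 12% at 20%, 22% at 25%, 41% at 33%, 59% at 40% and 79% at 50%. These figures assume the stated rates, independent patients, six evaluable patients where needed, and Table 7 governing the decisions. They give the chance of reaching the unwritten case, not a chance of harm or of a wrong decision. At low DLT rates the case is rare.

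The closing sentence also sits badly with Table 7 after 1 DLT in 3, which is already one third. The contradiction described here remains however that is settled.

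**What to change.** Two passages need reconciling, and which rule applies is for the sponsor to decide:

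1. Reconcile the closing sentence of Section 3.5 with the six-patient MTD requirement in Table 7 (and the matching definitions in Sections 3.1.1 and 3.4), so that one MTD rule remains.
2. Reconcile Table 7's step-down actions with the two-level design in Table 6 and Section 9.2, and state what the protocol concludes about the MTD when the de-escalation condition is met at level -1.

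Table 1's Arm D maximum and the two-to-three-level wording in Section 9.3 should be aligned at the same time.

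The cost is about one table row and one sentence. No new patients or procedures are needed. The downside is that, depending on the sponsor's choice, Arm D may formally end without an MTD.

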3.1.1 Part I: Dose Escalation or Dose De-Escalation (Part D Only)

A standard “3+3” study design will be used for this study. Patients enrolled at each dose level in Arm D will be evaluated for dose-limiting toxicity (DLT) for the purpose of determining the MTD. For Arm D, dose de-escalation will occur at the planned dose levels until the MTD is determined. The MTD is defined as the highest dose level with less than 2 patients with DLT out of at least six patients in the cohort. Management

and dose modifications associated with adverse events are outlined in subsequent protocol sections.

Two dose levels may be examined during the dose de-escalation with a standard “3+3” design, and a total of 3-6 patients will be enrolled per dose level. The de-escalation will be conducted as shown in Table 2 to evaluate the safety, tolerability, and MTD in patients with or metastatic solid tumors.

Table 2: Dosing Pattern of Avelumab in Combination with Other Cancer Immunotherapies with or without XRT.

Categories	Treatment Arm	Treatment	De-Escalation	Fixed Dose
I. Avelumab + Checkpoint Agonist(s)	A	Avelumab + Utomilumab (4-1BB)	MTD from Pfizer	
	B	Avelumab + PF-04518600 (OX40)	MTD from Pfizer	
	C	Avelumab + Utomilumab (4-1BB) + PF-04518600 (OX40)	MTD from Pfizer	
II. Avelumab + Checkpoint Agonist(s) + XRT	D	Avelumab + Utomilumab (4-1BB) + XRT	XRT**	Utomilumab (4-1BB) + Avelumab

**Dose de-escalation

Arm D will have de-escalation of radiation schedules.

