3.4 Maximum Tolerated Dose (MTD) Definition

In the Dose De-Escalation cohorts, patients will be assigned sequentially into cohorts of up to six patients in each cohort. Three to six patients will initially be enrolled in each cohort for DLT observation. A total of six patients will be enrolled in a cohort in the event that a DLT is observed in one of the first three patients and/or additional safety data are needed.

The MTD is defined as the highest dose level with less than 2 patients with DLT out of at least six patients in the cohort. Management and dose modifications associated with adverse events are outlined in subsequent protocol sections.

For all Arms, the DLT assessment window is 56 days (from Cycle 1 Day 1). In the absence of DLTs, patients continue consecutive treatment. For patients who experience a DLT, they may continue treatment with modifications if the toxicity resolves and at discretion of the attending physician and PI. In the absence of clinical deterioration and if the investigator believes that the patient continues to receive benefit from the treatment, patients may continue to receive study drug combinations after the first indication of progressive disease until a confirmation scan is obtained.

To understand and safeguard against potential cumulative toxicities the study team will continue to monitor the occurrence of study drug related SAEs and AEs throughout the treatment period and during potential treatment extensions to allow for dose correction in the event of cumulative immune-mediated toxicities.

Delayed onset of significant toxicity at the discretion of the investigator will be evaluated on a case-by-case basis upon consultation between the IND Office, Pfizer, and the principal investigator. At minimum, a review and discussion of potential delayed onset of significant toxicity will take place at each cohort review prior to a dose escalation decision.

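### Section 3.5's one-third rule contradicts Table 7 at 1 DLT in 3, and on any reading it names the untested 21 Gy level as the MTD

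*Combined protocol and SAP*

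**What the plan says.** Arm D starts at level 1 (24 Gy) and has one lower level, -1 (21 Gy), with the same drug doses at both (Section 3.2.4, Table 6). Section 3.2.4 states that de-escalation was re-started under Amendment 09.

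Four places handle 1 DLT in 3 by expanding the cohort or define the MTD on six patients:

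- Table 7, row for 1 of 3: "Enter at least 3 more patients at this dose level. If 0 of these 3 patients experience DLT", that level is the MTD.
- The sentence in Section 3.5 just before the disputed one, for a DLT in a cohort of three: "3 additional patients will be enrolled in that cohort".
- Section 3.4: "six patients will be enrolled in a cohort in the event that a DLT is observed in one of the first three patients".
- The MTD definition in Section 3.1.1, repeated in 3.4 and 3.5: "less than 2 patients with DLT out of at least six patients in the cohort". Table 7 adds: "Six patients should be treated before the dose is declared the MTD".

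The last sentence of Section 3.5 sets a different rule: "If at any time more than or equal to one third (33%) of the participants at a dose level experience DLT", then "the MTD will be reassessed" and "the next lowest dose level for the combination therapy will be considered the MTD". It gives no minimum number of patients at the failing level and none at the lower level.

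Sections 3.3 and 9.2 separately stop an expansion cohort when the aggregate DLT rate exceeds 33%. They do not say what then becomes the MTD.

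**The concern.** The last sentence can be read in two ways.

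**Literal reading.** It applies at any time, so 1 of 3 triggers it and level 1 is lost. Table 7 would treat three more and keep level 1 if none of them had a DLT. The data 1/3 then 0/3 give a 24 Gy MTD under Table 7 and a 21 Gy MTD under the last sentence.

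**Later-check reading.** Saying that the MTD is reassessed may limit the sentence to the period after an MTD is set. The fate of level 1 then agrees with Table 7. The sentence still declares level -1 the MTD. Level -1 opens only if level 1 fails, so at that moment nobody in the re-started de-escalation has been treated there. When a level fails, Table 7 enters three patients at the lower level; it does not declare that level the MTD.

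Estimating the MTD and selecting the RP2D in Arm D is a primary objective. An MTD is also what opens an expansion of up to 14 patients (Sections 3.1.2 and 3.2.4).

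**Working it through.** **Inputs.** Table 7 and the last sentence of Section 3.5; two levels of up to six patients (Section 9.3: 2 × 6 = 12, which reproduces); an expansion of up to 14; Phase II reviews every 7 evaluable patients (Section 9.3). The protocol gives no expected DLT rate, so the true rate p is assumed at 5, 10, 20, 30 and 40%, with q = 1 − p.

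**Threshold.** 1/3 = 33.3% meets the limit; 1/6 = 16.7% does not; 2/6 = 33.3% does. With six patients the two rules agree. They disagree at three.

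**Level 1 kept.**

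- Table 7: T = q³·P(Bin(3,p) ≤ 1) + 3pq²·q³. The second term is the path 1/3 then 0/3.
- Literal sentence: L = q³·P(Bin(3,p) ≤ 1). The result is the same if the limit is checked after every patient.
- Gap: T − L = 3pq⁵. At p = 0.20: 3 × 0.2 × 0.8⁵ = 0.197.

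**Different declared result** (level 1, level -1 or no MTD). The literal sentence also names level -1 where Table 7 would fail both levels. If level -1 has the same DLT rate, this adds (1 − T)². If level -1 never fails, it adds nothing, and the difference is T − L.

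| p | T | L | T − L | 1 − T (level -1 fails if tested, equal rate) | (1 − T)² | Result differs, equal rate |
|---|---|---|---|---|---|---|
| 0.05 | 0.967 | 0.851 | 0.116 | 0.033 | 0.001 | 0.117 |
| 0.10 | 0.886 | 0.709 | 0.177 | 0.114 | 0.013 | 0.190 |
| 0.20 | 0.655 | 0.459 | 0.197 | 0.345 | 0.119 | 0.315 |
| 0.30 | 0.420 | 0.269 | 0.151 | 0.580 | 0.336 | 0.487 |
| 0.40 | 0.233 | 0.140 | 0.093 | 0.767 | 0.588 | 0.681 |

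**Later-check reading.** Start from 0/6 or 1/6 at level 1 (Table 7 passed), add 14 expansion patients, and stop when 3 × DLTs ≥ n. The probability of passing Table 7 and then reaching one third is:

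| p | Checked after each patient | Checked only after 7 and 14 (n = 13, 20) | Mean expansion slots used at breach (each-patient check) |
|---|---|---|---|
| 0.05 | 0.002 | 0.0001 | 3.3 |
| 0.10 | 0.015 | 0.0015 | 4.1 |
| 0.20 | 0.085 | 0.028 | 5.2 |
| 0.30 | 0.154 | 0.089 | 5.7 |
| 0.40 | 0.151 | 0.117 | 5.6 |

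**Overlap with the expansion stopping rule.** For every n from 3 to 20, the smallest DLT count above 33% equals the smallest count at or above one third (for example 2 at n = 6, 5 at n = 13, 7 at n = 20). A breach during expansion at level 1 already stops enrolment under Sections 3.3 and 9.2. On this reading, all that the last sentence adds is the MTD label for level -1.

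**The case against.** The strongest reply is that nobody would apply the sentence literally. Section 3.5 introduces Table 7 as the rule for de-escalation decisions, Section 9.2 again refers to a standard 3+3, and the preceding sentence enrols three more patients at 1 of 3. Reassessing an MTD presupposes that one exists. This stands as a reason to think the later-check reading was intended, and the 9 to 20 point gap belongs only to the literal reading. But the text says the limit applies at any time and states no precedence between the rules.

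Second, the largest figure (68%) requires the literal reading, equal toxicity at 21 and 24 Gy, and no later correction. At p = 0.40, 59 of those points come from both levels failing. The expansion stopping rule would also act at level -1. In a 14-patient expansion there it stops 50% of cohorts at p = 0.30 and 77% at p = 0.40 if checked at 7 and 14, or 79% and 92% if checked after each patient from the third. This stands: many intolerable levels would be found later. The level would nevertheless have been declared the MTD first.

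Third, any error is towards 3 Gy less radiation with unchanged drug doses. The IND Medical Monitor approves each change of level, and the RP2D also draws on efficacy and expansion data. All true, and it limits the safety concern. None of it settles which rule determines the MTD.

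Finally, level -1 could be taken as only a candidate, with Table 7 then applied there. That is a sensible design, but it is not what "the next lowest dose level for the combination therapy will be considered the MTD" says.

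**Conclusion.** The concern holds. On the literal reading, identical data can give 24 Gy or 21 Gy as the MTD. The rules differ on level 1 with probability 3pq⁵, which is 12, 18, 20, 15 and 9% at true DLT rates of 5, 10, 20, 30 and 40%. On the later-check reading the remaining fault is narrower and less frequent: an MTD label on a level with no patients on the current schedule, reached in 0.2 to 15% of trials if checked after each patient, or 0.01 to 12% if checked every 7. On either reading a 21 Gy MTD could be reported that fails the protocol's own definition.

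All probabilities rest on assumed DLT rates and independent patients. The 12 to 68% range for a different declared result also assumes equal rates at both levels. The issue concerns Arm D only, since Arms A to C take their MTD from Pfizer. It should be corrected because it makes the decision rule for a primary objective ambiguous, not because it exposes patients to a higher dose.

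**What to change.** Amend the end of Section 3.5:

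1. Apply the one-third limit only once six evaluable patients have been treated at the level, so that 1/6 passes and 2/6 fails, as in Table 7. Keep Table 7's de-escalation at two or more DLTs.
2. Replace the statement that the next lowest level is considered the MTD with one that this level is opened, and needs six evaluable patients with no more than 1 DLT before it is declared the MTD.

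The cost is a few sentences. After a breach in expansion at level 1, up to six patients are needed at level -1; these fit within the 12 de-escalation patients planned in Section 9.3.

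Two optional clarifications would help. First, state whether unused expansion slots move to level -1. With a check after each patient, a breach uses on average about 3 to 6 of the 14 slots and leaves about 8 to 11; checks only every 7 patients would leave 7 or none. Moving only the unused slots keeps Arm D within 6 + 6 + 14 = 26 patients under Amendment 09, which matches Table 12 (33 less the 7 earlier patients). Restarting a full expansion could take 6 + 14 + 6 + 14 = 40. Second, state that if level -1 fails, no MTD is declared and Arm D does not expand, which already follows from Sections 3.1.2 and 3.2.4.
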